6.6.1. Dose Interruptions

Following initiation of therapy, treatment with encorafenib may be delayed to allow resolution of toxicity. Participants may resume treatment if no medical condition or other circumstance exists that, in the opinion of the investigator, would make the participant unsuitable for further participation in the study.

Dose interruptions are permitted in the case of medical/surgical events or logistical reasons not related to study treatment (e.g. elective surgery, unrelated medical events, vacation, holidays). Participants should be resumed on study treatment within 2 weeks (14 days) of the scheduled interruption, unless otherwise discussed with the sponsor. The reason for interruption will be documented in the participant's medical file and in the eCRF.

If a participant misses >4 weeks (i.e. 28 consecutive days) of dosing with encorafenib, study treatment will be permanently discontinued (see **Section 7.1**).

6.6.2. Dose Reductions

The dose of encorafenib may be reduced for toxicity management as outlined in **Table 7**. All dose modifications are based on the worst preceding toxicity. Dose reduction below 150 mg QD encorafenib is not allowed.

Table 7: Dose Reductions for Encorafenib

Dose Level	Encorafenib
0 (starting dose)	300 mg QD
-1	225 mg QD
-2	150 mg QD

Abbreviations: QD = once daily
NOTE: Dose reduction should be based on the highest preceding toxicity

If the event causing a dose reduction improves to the baseline level and remains stable for a minimum of 14 days, the dose can be re-escalated to the next dose level at the discretion of the investigator, provided there are no other concomitant toxicities that would prevent re-escalation. There is no limit to the number of times the participant can have their dose reduced or re-escalated (in increments specified in Table 7).

Following any dose reductions occurring due to toxicity, should investigators believe that it is the best interest of their patients, they may re-start and re-escalate doses, with close supervision and monitoring of their patients, except for the following circumstances of dose modification:

- No dose re-escalation of encorafenib is allowed after a dose reduction due to prolonged QTcF \geq 501 msec
- No dose re-escalation is allowed after a dose reduction due to retinal toxicity \geq Grade 2.

7. Discontinuation of Study Treatment and Participant Discontinuation/Withdrawal

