7.1.2. Permanent Study Treatment Discontinuation

Study treatment is to be administered until any of the following criteria for permanent discontinuation is met:

- Disease progression, as defined by Response Evaluation Criteria in Solid Tumors (RECIST) Version 1.1 (continuation of treatment beyond progression is permitted in special circumstances, see **Section 6.1**).

- Clinical progression, as determined by the investigator in the absence of radiographic progression.
- Withdrawal of consent. Participants may choose to withdraw consent to continue study treatment but remain in the study to be followed for safety and disease progression. In this case, follow-up data will continue to be collected for this participant. Withdrawal of consent for study treatment may occur at any time without penalty of jeopardizing their healthcare or loss of benefits to which they are otherwise entitled. Participants who withdraw consent to study treatment and follow-up, will no longer receive study treatment or followed up within this study.
- Unacceptable adverse events or failure to tolerate study treatment:
 - Grade 4 or life-threatening adverse event as outlined in Appendix 10.4 (except with approval from the sponsor's medical monitor)
 - Toxicity requiring more than the allowed number of dose reductions for encorafenib, (see **Table 7**).
 - Occurrence of an adverse event that is related to study treatment and compromises the participant's ability to continue study-specific procedures according to investigator's judgement or is considered to not be in the participant's best interest. The medical monitor or delegate should immediately be informed by phone or e-mail and a report explaining the discontinuation will be forwarded to him/her as soon as possible.
- Initiation of subsequent anticancer therapy.
- Participant is non-compliant with study procedures or study treatment that in the judgment of the investigator or sponsor renders the participant unsuitable.
- Significant protocol deviation that, in the opinion of the investigator and/or sponsor, renders the participant unsuitable for further study treatment administration.
- Participant has missed >4 weeks (i.e., 28 consecutive days) of dosing (see Section 7.1.1).
- Participant becomes pregnant or begins breastfeeding.
- Participant is lost to follow-up.
- Defined end of the study (see Section 4.4)

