Grade 2	
1st occurrence:
 
Maintain dose of encorafenib and HFSR should be closely monitored. Promptly institute supportive measures, such as topical therapy, for symptomatic relief. Give instruction on lifestyle modifications.
 
If no improvement ≤ 14 days, interrupt dosing of encorafenib until resolved to Grade ≤ 1. Resume treatment with encorafenib at current dose level. Continue supportive measures, such as topical therapy, for symptomatic relief. Give instruction on lifestyle modifications.
 
Additional occurrence:
 
Treatment with encorafenib may be maintained or interrupted based upon the investigator's discretion. Continue supportive measures, such as topical therapy, for symptomatic relief. Give instruction on lifestyle modifications.
 
If dosing is interrupted, interrupt until resolved to Grade ≤ 1. Resume study treatment at the same dose level or one reduced dose level[a] of encorafenib at the investigator's discretion.

Worst Toxicity NCI CTCAE Version 4.03 Grade (unless otherwise specified)	Dose Modification for Encorafenib
Grade 3	
1st to 3rd occurrence: Interrupt dosing of encorafenib until resolved to Grade ≤ 1. Promptly initiate supportive measures, such as topical therapy, for symptomatic relief. Give instruction on lifestyle modifications. Reassess the participant weekly. Then resume treatment at one reduced dose level[a] of encorafenib. Consider referral to dermatologist and manage HFSR per dermatologist's recommendation.
 
>3rd occurrence: Interrupt dosing of encorafenib until resolved to Grade ≤ 1, decision to resume treatment with encorafenib at one reduced dose level[a] or permanently discontinue encorafenib should be based upon the investigator's discretion.

SCC, KA and any Other Suspicious Skin Lesion	
Grade ≤ 3	Maintain dose of encorafenib. Treatment of SCC, KA and any other suspicious skin lesion (e.g. new primary melanoma) should occur based upon study site standards.
Diarrhea. Treatment should be based on study site practice	
Uncomplicated Grade 1 or 2	Maintain dose of encorafenib.
Complicated Grade 1 or 2	Consider temporary interruption of encorafenib until resolved to Grade ≤ 1 . Then resume treatment at current dose level.

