Grade 3 or 4	Interrupt dosing of encorafenib until resolved to Grade ≤ 1 . Then resume treatment at current dose level of encorafenib if, in the judgment of the investigator, the toxicity is considered to be unrelated to encorafenib, or at one reduced dose level[a].
Nausea/vomiting	
Grade 1 or 2	Maintain dose level of encorafenib. Promptly institute antiemetic measure.
Grade 3	Interrupt dosing of encorafenib until resolved to Grade ≤ 1 . Then resume treatment at one reduced dose level[a] of encorafenib. Note: Interrupt dosing of encorafenib for \geq Grade 3 vomiting or Grade 3 nausea only if the vomiting or nausea cannot be controlled with optimal antiemetics (based on study site standards).
Grade 4	Permanently discontinue encorafenib[e].
All other adverse events (suspected to be related to encorafenib)	
Grade 1 or 2	If the event is a persistent Grade 2 adverse event not responsive to a specific therapy, consider interruption or reduction of encorafenib, as applicable
Grade 3	Interrupt dosing of encorafenib until resolved to Grade ≤ 1 or to pretreatment/baseline level. If the event resolves ≤ 21 days, then encorafenib may be resumed at one reduced dose level[a] based upon the investigator's discretion.
Grade 4	Permanently discontinue encorafenib[e].

Abbreviations: ALT = alanine aminotransferase; AST = aspartate aminotransferase; CK = creatine kinase; HFSR = hand-foot skin reaction; KA = keratoacanthoma; NCI CTCAE = National Cancer Institute Common Terminology Criteria for Adverse Events; PPE = Palmar-plantar erythrodysesthesia; QTcF = QT interval corrected for heart rate using Fridericia's formula; SCC = squamous cell carcinoma; ULN = upper limit of normal.
 
[a] Dose reduction below 150 mg QD is not allowed.
	

Worst Toxicity NCI CTCAE Version 4.03 Grade (unless otherwise specified)	Dose Modification for Encorafenib

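### The Table 19 instruction for a third Grade 3 hand-foot skin reaction cannot be carried out within Table 7 unless the dose has been re-escalated, and the 'allowed number' of reductions in Section 7.1.2 is undefined

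*Protocol*

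**What the plan says.** - **Protocol 6.6.2** gives the ladder in "Table 7: Dose Reductions for Encorafenib": 300 mg, then 225 mg, then 150 mg once daily. It sets a floor: "Dose reduction below 150 mg QD encorafenib is not allowed". After at least 14 stable days, "the dose can be re-escalated to the next dose level at the discretion of the investigator". It adds "There is no limit to the number of times the participant can have their dose reduced or re-escalated", and that sentence goes on to tie the changes to Table 7 increments.
- **Protocol 7.1.2** lists among the grounds for permanent discontinuation "Toxicity requiring more than the allowed number of dose reductions for encorafenib", with a pointer to Table 7. Table 7 lists dose levels and states no number.
- **Protocol Appendix 10.4, Table 19, Grade 3 HFSR** has two lines. For "1st to 3rd occurrence" the site interrupts dosing until Grade 1 or better, then resumes one level lower; stopping is not offered. After the third occurrence, the "decision to resume treatment with encorafenib at one reduced dose level[a] or permanently discontinue encorafenib" is left to the investigator.
- **Footnote [a] of Table 19**, attached to both lines, says "Dose reduction below 150 mg QD is not allowed". It does not say what happens to a participant already at 150 mg.

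**The concern.** The HFSR row directs three reductions on a ladder that has two. A participant who reaches 150 mg and then has a third Grade 3 event meets three texts that do not agree: the row says resume lower, the floor forbids it, and 7.1.2 points to stopping. Separately, 7.1.2 presupposes a limit on the number of reductions, while 6.6.2 says the number is unlimited.

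What is at stake is first whether such a participant continues or stops, and whether two sites would decide alike. The analysis follows from that. Adverse events leading to discontinuation are part of a secondary endpoint, and the reason for stopping, duration of exposure and dose intensity are all summarised (SAP 5.2, 5.6.1 and 5.6.2).

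**Working it through.** No sample size, power or error rate bears on this point. The check is a count of steps and a comparison of the texts.

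**Inputs.** Starting dose 300 mg, step 75 mg, floor 150 mg (Protocol 6.6.2, Table 7). One reduction at each of occurrences 1, 2 and 3 (Table 19, Grade 3 HFSR). Re-escalation between occurrences is optional (6.6.2); its two stated exceptions concern QTcF and retinal toxicity, not HFSR.

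**Steps available.** (300 − 150) / 75 = 2.

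**Steps directed by the third occurrence.** 3. Without re-escalation: 300 − 3 × 75 = 75 mg, which is below 150 mg.

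**All three-occurrence paths.** Allow no re-escalation, one level or two levels between events (an upward arrow marks re-escalation):

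| Path | Third reduction possible? | Reductions directed |
|---|---|---|
| 300→225→150→(75) | No, below floor | 3 |
| 300→225→150↑225→150 | Yes | 3 |
| 300→225→150↑300→225 | Yes | 3 |
| 300→225↑300→225→150 | Yes | 3 |
| 300→225↑300→225↑300→225 | Yes | 3 |

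Four of the five paths can be carried out. This counts paths; it is not a probability.

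**Set against 7.1.2.** The allowed number can be read in two ways.

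- *Cumulative count of two.* All five paths exceed it at the third reduction, so 7.1.2 says stop. On the last four paths 6.6.2 and Table 19 say continue.
- *Depth of two levels.* Only the first path exceeds it. On the other four, 7.1.2, 6.6.2 and Table 19 agree.

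On the first path both readings of 7.1.2 lead to stopping, while the Table 19 line directs resumption. That conflict therefore does not depend on how the allowed number is read. On the other four paths a conflict exists only under the count reading.

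**Comparison within Table 19.** The row for QTcF above 500 ms with a change of at most 60 ms reduces at the first and second occurrences and discontinues at the third, which fits two levels. The HFSR line beyond the third occurrence can also be carried out at 150 mg, because it offers stopping. Only the third-occurrence instruction breaks.

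**The case against.** The strongest reply is that the texts fit together if read sensibly: reduce as often as needed, never more than two levels below the start, and stop if toxicity calls for less. Table 7 holds levels rather than a lifetime count, so its use in 7.1.2 favours this reading. Footnote [a] carries the floor into the HFSR row. Table 19 is headed as recommended modifications and Section 6.6 leaves room for clinical judgement, so a site is not stranded.

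Much of this stands. A reader might infer that 6.6.2 sets no limit on reductions; it limits depth through the floor. A reader might infer that 6.6.2 and 7.1.2 flatly contradict each other; they do so only if the allowed number means a cumulative two, which no text states. A reader might infer that sites have no workable instruction at any third HFSR event; four of five paths have one.

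Two things remain. The reconciling reading is nowhere written down. And it does not repair the HFSR row: under it the first path ends in stopping at the third event, whereas the row directs resumption and mentions stopping only later. Footnote [a] forbids a dose but supplies no action.

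**Conclusion.** The concern holds in two parts of unequal strength. The third-occurrence HFSR instruction cannot be carried out for a participant not re-escalated in between, and it conflicts with 7.1.2; this is an internal contradiction. The meaning of the allowed number is an ambiguity, not an established contradiction.

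The size is modest. A participant with recurrent HFSR is already counted under adverse events leading to reduction at the first one, so the participant count there does not move. The discontinuation count can. One participant is 1/6 = 17% to 1/3 = 33% of a denominator of six or three, as for any event in a trial this small. Exposure and dose intensity also depend on the choice: a site that kept the participant at 150 mg would add days at 150/300 = 50% of planned intensity, whereas stopping ends the exposure interval.

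It is tempting to say that the tolerability decision or primary endpoint is at risk. The documents do not support that. DLTs are judged on the event in Days 1 to 28, and the Trial Steering Committee assesses tolerability on Cycle 1. Re-escalation needs at least 14 stable days, and each Grade 3 episode requires an interruption, so I assume that three such reductions will rarely fall within 28 days. The later committee meeting receives no statistical outputs (SAP 1.2).

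Nor does the 52% for palmar-plantar erythrodysesthesia in Protocol 2.1.4 measure how often this would arise. It is an any-grade figure for events described there as generally low grade. The frequency of a third Grade 3 episode is unknown from these documents.

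**What to change.** Reconcile Protocol 6.6.2, 7.1.2, Table 7 and the Grade 3 HFSR row of Table 19 with footnote [a]:

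1. State once what the allowed number of reductions means, as a cumulative count or as levels below the starting dose, and use that meaning in 6.6.2 and 7.1.2.
2. Reword the HFSR occurrence lines so that each can be carried out within Table 7, including for a participant already at 150 mg, and cross-refer them to 7.1.2.

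Which rule applies is the sponsor's clinical decision, and this review takes no position on it. The cost is a clarification amendment to the protocol wording, with no added procedures or visits.

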7.1. Discontinuation of Study Treatment for Individual Participants

7.1.1. Temporary Discontinuation and Rechallenge

Adverse events and clinically significant laboratory abnormalities leading to a dose interruption and the conditions for re-starting study treatment (rechallenge) are provided in Appendix 10.4.

A treatment interruption occurs if at least one study treatment administration is missed, followed by a restart of the study treatment.

It may be necessary for a participant to interrupt study treatment to allow for resolution of toxicity (see Section 6.6). Participants may resume treatment if no medical condition or other circumstance exists that, in the opinion of the investigator, would make the participant unsuitable for further participation in the study.

Dose interruptions are also permitted in the case of medical/surgical events or logistical reasons not related to study treatment (e.g. elective surgery, unrelated medical events, vacation, holidays). Participants should be resumed on study treatment within 2 weeks (14 days) of the scheduled interruption, unless otherwise discussed with the Sponsor. The reason for interruption will be documented in the eCRF. Dose interruptions of >4 weeks (28 consecutive days) are not allowed unless approved by the sponsor's medical monitor and study treatment must be permanently discontinued (see **Section 7.1.2**).

7.1.2. Permanent Study Treatment Discontinuation

Study treatment is to be administered until any of the following criteria for permanent discontinuation is met:

- Disease progression, as defined by Response Evaluation Criteria in Solid Tumors (RECIST) Version 1.1 (continuation of treatment beyond progression is permitted in special circumstances, see **Section 6.1**).

- Clinical progression, as determined by the investigator in the absence of radiographic progression.
- Withdrawal of consent. Participants may choose to withdraw consent to continue study treatment but remain in the study to be followed for safety and disease progression. In this case, follow-up data will continue to be collected for this participant. Withdrawal of consent for study treatment may occur at any time without penalty of jeopardizing their healthcare or loss of benefits to which they are otherwise entitled. Participants who withdraw consent to study treatment and follow-up, will no longer receive study treatment or followed up within this study.
- Unacceptable adverse events or failure to tolerate study treatment:
 - Grade 4 or life-threatening adverse event as outlined in Appendix 10.4 (except with approval from the sponsor's medical monitor)
 - Toxicity requiring more than the allowed number of dose reductions for encorafenib, (see **Table 7**).
 - Occurrence of an adverse event that is related to study treatment and compromises the participant's ability to continue study-specific procedures according to investigator's judgement or is considered to not be in the participant's best interest. The medical monitor or delegate should immediately be informed by phone or e-mail and a report explaining the discontinuation will be forwarded to him/her as soon as possible.
- Initiation of subsequent anticancer therapy.
- Participant is non-compliant with study procedures or study treatment that in the judgment of the investigator or sponsor renders the participant unsuitable.
- Significant protocol deviation that, in the opinion of the investigator and/or sponsor, renders the participant unsuitable for further study treatment administration.
- Participant has missed >4 weeks (i.e., 28 consecutive days) of dosing (see Section 7.1.1).
- Participant becomes pregnant or begins breastfeeding.
- Participant is lost to follow-up.
- Defined end of the study (see Section 4.4)
- Termination of the study site or study by the sponsor/competent authority (described in **Appendix 10.1.2 and Appendix 10.1.10**).
- Physician decision.
- Other reasons (any unexpected event considered relevant by the investigator to be discussed case by case with the sponsor).

If a participant is withdrawn from study treatment, the date and reason of treatment discontinuation will be recorded in the eCRF. The participant will have an end of treatment visit followed by a 30-day safety follow-up assessment.

Data to be collected at the time of discontinuation of study treatment and follow-up and for any further evaluations that need to be completed are specified in Table 1. For participants who have discontinued study treatment for reasons other than disease progression, tumor assessments should continue to be performed (as per local review and standard of care) until the start of a new anticancer therapy, disease progression, death, loss to follow-up, participant's decision or withdrawal of consent whichever occurs first.

Participants who are discontinued from the study treatment due to a treatment-related adverse event will be followed until resolution to Grade ≤ 1 or stabilization.

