6.6. Dose Modification

Participants will be monitored for adverse events throughout the study. The severity of adverse events will be graded according to National Cancer Institute Common Terminology Criteria for Adverse Events NCI CTCAE Version 4.03 [NCI CTCAE 2010].

If a participant develops toxicity, the dose should be modified as outlined in Appendix 10.4. This table include criteria for interruption, reduction and discontinuation of study treatment. All dose modifications should be based on the worst preceding toxicity. All dosing interruptions and modifications must be recorded in the eCRF.

Individual decisions regarding dose modifications should be made using appropriate clinical judgment, considering relatedness of the adverse event to the study treatment and the participant's underlying condition. Adverse events that have a clear alternative explanation or are transient (≤ 72 hours) abnormal laboratory values without associated clinically significant signs or symptoms may be exempt from dose reduction rules. The investigator should follow the study site supportive guidelines for the management of these toxicities and prophylactic measures.

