
 When an adverse event/SAE occurs, it is the responsibility of the investigator to review all documentation (e.g. hospital progress notes, laboratory reports and diagnostics reports) related to the event. For a recurrent adverse event (that resolves and subsequently recurs), each recurrence must be recorded as a separate adverse event. For a continuous adverse event (i.e. unresolved between participant assessments), any change in intensity (improvement or worsening) or seriousness must be recorded with the indication of the start and (if applicable) the end of the change within the same adverse event report. The investigator will then record all relevant adverse event/SAE information in the eCRF. It is not acceptable for the investigator to send photocopies of the participant's medical records to the sponsor or designee in lieu of completion of adverse event/SAE eCRF pages. There may be instances when copies of medical records for certain cases are requested by sponsor or designee. In this case, all participant identifiers, with the exception of the participant number, will be redacted on the copies of the medical records before submission. The investigator will attempt to establish a diagnosis of the event based on signs, symptoms and/or other clinical information. Whenever possible, the diagnosis (not the individual signs/symptoms) will be documented as the adverse event/SAE.
Assessment of Intensity

The investigator will make an assessment of intensity for each adverse event/SAE. Wherever possible this should be performed using the NCI CTCAE Version 4.03 scale [NCI CTCAE 2010]. For any term not specifically listed, intensity should be assigned as Grade 1 through 5 according to the following categories:
 
 Grade 1 (mild): asymptomatic or mild symptoms; clinical or diagnostic observations only; treatment not indicated. Grade 2 (moderate): minimal, local or non-invasive treatment indicated; limiting age-appropriate instrumental activities of daily living. Grade 3 (severe or medically significant but not immediately life-threatening): hospitalization or prolongation of hospitalization indicated; disabling; limiting self-care activities of daily living. Grade 4 (life-threatening consequences): urgent treatment indicated. Grade 5 (death related to adverse event).

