10.4. Appendix 4: Dose Modifications for Encorafenib-related Adverse Events

Table 19: Recommended Dose Modifications for Encorafenib-related Adverse Events

Worst Toxicity NCI CTCAE Version 4.03 Grade (unless otherwise specified)	Dose Modification for Encorafenib
Eye disorders - Posterior uveitis (including iritis and iridocyclitis)	
Any visual acuity impairment at screening should be documented and should be considered as baseline.	
Grade 1 or 2	
Treat with specific (e.g. topical) ocular therapy. If uveitis does not respond, interrupt dosing of encorafenib and repeat ophthalmic monitoring including visual acuity assessment within 10 days.
 
If resolved to baseline or \leqGrade 1 resume study treatment at the same dose.
 
If posterior uveitis lasts >6 weeks, permanently discontinue encorafenib.

Grade 2	
Treat with specific (e.g. topical) ocular therapy. If uveitis does not respond, interrupt dosing of encorafenib and repeat ophthalmic monitoring including visual acuity assessment within 10 days.
 
If resolved to \leqGrade 1, resume study treatment at one reduced dose level of encorafenib[a].
 
If posterior uveitis lasts >6 weeks, permanently discontinue encorafenib and ophthalmic monitoring should be repeated.

Grade 3	
Interrupt dosing of encorafenib and repeat ophthalmic monitoring including visual acuity assessment within 10 days.
 
If resolved to \leqGrade 1, resume study treatment at one reduced dose level of encorafenib[a].
 
If posterior uveitis lasts >6 weeks, permanently discontinue encorafenib and ophthalmic monitoring should be repeated.

Grade 4	Permanently discontinue encorafenib and immediately follow-up with ophthalmic monitoring[b]
Liver-related adverse events	
Grade 1 AST or ALT $>ULN$ to $3 \times ULN$	Maintain dose level of encorafenib.
Grade 2 AST or ALT >3 to $5.0 \times ULN$ or $3 \times$ baseline value[c] AND blood total bilirubin $\leq 2.0 \times ULN$	
Maintain dose level of encorafenib.
 
If not resolved in ≤ 14 days, interrupt dose of encorafenib until resolved to Grade ≤ 1 (or Grade ≤ 2 in case of liver metastasis), then resume study treatment at current dose level of encorafenib.
 
If additional occurrence:
 
Interrupt dosing of encorafenib until resolved to Grade ≤ 1 (or Grade ≤ 2 in case of liver metastasis), then resume study treatment at one reduced dose level[a] of encorafenib.

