AST or ALT 3.0 to $5.0 \times ULN$ AND blood total bilirubin $>2.0 \times ULN$	
Interrupt dosing of encorafenib until resolved to Grade ≤ 1, then:
 
 • If resolved in ≤ 7 days, resume study treatment at one reduced dose level[a] of encorafenib. • If not resolved in ≤ 7 days, permanently discontinue encorafenib.

Worst Toxicity NCI CTCAE Version 4.03 Grade (unless otherwise specified)	Dose Modification for Encorafenib
Grade 3 AST or ALT >5.0 to $8.0 \times$ ULN AND blood total bilirubin $\leq 2.0 \times$ ULN	
Interrupt dosing of encorafenib until resolved to Grade ≤ 1 (or Grade ≤ 2 in case of liver metastasis), then:
 
 • If resolved in ≤ 14 days, resume study treatment at current dose level of encorafenib. • If not resolved in ≤ 14 days, resume study treatment at one reduced dose level[a] of encorafenib. 
If additional occurrence: Interrupt dosing of encorafenib until resolved to Grade ≤ 1 (or Grade ≤ 2 in case of liver metastasis), then resume treatment at one reduced dose level[a] of encorafenib.

AST or ALT $>8 \times$ ULN AND blood total bilirubin $\leq 2.0 \times$ ULN	Permanently discontinue encorafenib.
AST or ALT $>5.0 \times$ ULN AND blood total bilirubin $>2.0 \times$ ULN	Permanently discontinue encorafenib.
Grade 4 AST or ALT $>20.0 \times$ ULN	Permanently discontinue encorafenib.
Cardiac investigation – Prolongation of QT interval QTcF value	

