Grade 2	
Maintain dose level of encorafenib.
 
Initiate Initial Rash Treatment regimen if it was not already started and rash should be closely monitored.
 
Reassess within ≤ 14 days. If rash worsens or does not improve, interrupt dosing of encorafenib until resolved to Grade ≤ 1. Then resume study treatment at current dose level of encorafenib. For dermatitis acneiform, treatment with encorafenib may be maintained if, in the judgment of the investigator, the rash is considered to be unrelated to encorafenib. If treatment with encorafenib was maintained and no improvement within 8 days, interrupt dosing of encorafenib.

Grade 3	
1st occurrence:
 
Interrupt dosing of encorafenib until resolved to Grade ≤ 1. Reassess weekly. Then resume treatment at current dose level of encorafenib.
 
Consider referral to dermatologist and manage rash per dermatologist's recommendation.
 
2nd occurrence:
 
Interrupt dosing of encorafenib until resolved to Grade ≤ 1. Then resume study treatment at one reduced dose level[a] of encorafenib unless in the judgment of the investigator, the rash is considered to be unrelated to encorafenib then study treatment can be resumed at the same dose level.
 
Consider referral to dermatologist and manage rash per dermatologist's recommendation.

Grade 4	Permanently discontinue encorafenib[e].
HFSR/PPE syndrome[d]	
Grade 1	
Maintain dose of encorafenib. Promptly institute supportive measures, such as topical therapy, for symptomatic relief. Give instruction on lifestyle modifications.

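### Protocol Section 7.1.2 lets the medical monitor waive a Grade 4 stop without stated conditions, which does not match the restart rules in Table 19

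*Protocol*

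**What the plan says.** Section 7.1.2 of the protocol lists the criteria for permanent discontinuation. One of them is a "Grade 4 or life-threatening adverse event as outlined in Appendix 10.4 (except with approval from" the sponsor's medical monitor). The bullet names no recovery grade, time limit, restart dose or event type.

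Section 7.1.1 says that "the conditions for re-starting study treatment (rechallenge) are provided in Appendix 10.4". In that appendix, Table 19 treats Grade 4 events in three ways:

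- **Permanent stop, no restart route.** For Grade 4 posterior uveitis (a category that includes iritis and iridocyclitis) the instruction is "Permanently discontinue encorafenib and immediately follow-up with ophthalmic monitoring", with marker [b] only, which concerns eye monitoring. The row headed "Grade 4 AST or ALT" (above 20 × ULN) is a permanent stop with no footnote.
- **Permanent stop with marker [e].** This covers Grade 4 rash, nausea/vomiting and all other related events. Footnote [e] allows restart at the lower dose level if the event recovers to Grade 1 or less within 28 days. The investigator and the medical monitor must also consider that the event is not life-threatening and that the participant can be managed and monitored for recurrence.
- **Interruption.** Grade 3 or 4 diarrhea is interrupted and then resumed.

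**The concern.** The two places can give different answers to one safety question: may a participant be given encorafenib again after a Grade 4 event? A medical monitor working from Section 7.1.2 could approve restart after Grade 4 posterior uveitis or Grade 4 AST/ALT. One working from Table 19 would find no route to do so. For the three event types under [e], Section 7.1.2 does not say whether the conditions in [e] must be met.

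These toxicities are foreseen: Grade 4 ALT or AST and confirmed Grade 4 uveitis are both DLT criteria in Table 4. At stake are participant safety and consistent handling across the two or three sites.

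**Working it through.** No calculation is involved beyond a count. The check sets Section 7.1.2 against each row of Table 19 that names Grade 4, with AST/ALT counted once.

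| Event type | Grade 4 action | [e] attached? | Restart in Table 19 | Restart in 7.1.2 |
|---|---|---|---|---|
| Posterior uveitis | Permanent stop | No ([b] only) | None | With monitor approval |
| AST/ALT | Permanent stop | No | None | With monitor approval |
| Rash | Permanent stop | Yes | Under [e] | With monitor approval |
| Nausea/vomiting | Permanent stop | Yes | Under [e] | With monitor approval |
| All other related events | Permanent stop | Yes | Under [e] | With monitor approval |
| Diarrhea | Interruption | No | Yes, after recovery | Not a permanent stop |

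Count: 2 without [e] + 3 with [e] + 1 interruption = 6. The table names no Grade 4 row for hand-foot skin reaction or for squamous cell carcinoma/keratoacanthoma.

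**Could the exception in 7.1.2 simply mean footnote [e]?** Not for uveitis and AST/ALT, whose rows do not carry [e]. For the other three it could, since the bullet cites Appendix 10.4, but it does not say so. Two differences remain. The bullet asks only for the monitor's approval, whereas [e] adds the investigator's opinion, recovery within 28 days and a lower dose. The bullet also names life-threatening events, whereas [e] requires that the event be judged not life-threatening. That second difference may be only verbal. For terms not listed in CTCAE, Table 10 describes "Grade 4 (life-threatening consequences): urgent treatment indicated", so the two terms in the bullet may mean one thing. The text does not settle it.

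**Liver rows.** Table 19 has two further permanent-stop rows, neither with [e]:

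- AST/ALT above 8 × ULN with bilirubin at or below 2 × ULN;
- AST/ALT above 5 × ULN with bilirubin above 2 × ULN.

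Take bilirubin at or below 2 × ULN. A value of 10 × ULN is a permanent stop. It is below the table's Grade 4 threshold of 20 × ULN, so the exception in 7.1.2 does not reach it unless the event is otherwise life-threatening. A value of 25 × ULN is Grade 4, so the exception does reach it. If 7.1.2 overrides the table, the worse value can be waived and the lesser one cannot.

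Every value above 20 × ULN also meets one of these two rows. With bilirubin at or below 2 × ULN it exceeds 8 × ULN; with bilirubin above 2 × ULN it exceeds 5 × ULN.

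**Does Section 6.6 resolve this?** It has two relevant sentences. One calls for clinical judgment in decisions on dose modification and is not limited to reductions. The next covers events with a clear alternative explanation and transient laboratory values "without associated clinically significant signs or symptoms may be exempt from dose reduction rules". That exemption does not extend to permanent discontinuation.

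**The case against.** The strongest reply is that the two places work together as default and override. Table 19 is titled as *recommended* modifications for encorafenib-related events, and Section 6.6 asks for clinical judgment. On this view the table gives the usual action and the bracket in 7.1.2 allows a case-by-case exception. Footnote [e] also opens in general terms, so its absence from two rows may be a slip in placing markers. Nor is the monitor's discretion unlimited. Sections 6.6.1 and 7.1.1 require that nothing, in the investigator's opinion, makes the participant unsuitable to resume. More than 28 consecutive missed days is a separate stopping criterion in 7.1.2.

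Much of this stands. A reader might infer a flat contradiction that no reading can repair. The documents do not support that, because the override reading is available. It does not remove the problem, however. Section 7.1.1 places the restart conditions in Appendix 10.4, and note [a] to Table 8 places the liver stopping criteria and required actions there too. Footnote [e] spells out conditions that 7.1.2 omits. The override reading also produces the reversed order for liver values shown above, which is unlikely to be intended.

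Four further inferences should be resisted:

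- **All Grade 4 eye events are affected.** Only posterior uveitis, with iritis and iridocyclitis, lacks [e]. Other related eye events fall under the all-other row, which carries it.
- **A site could restart treatment alone.** The bracket requires medical-monitor approval.
- **The two routes lead to lasting dose differences.** The lower level in [e] is a restart dose. Under Section 6.6.2, once the event has been stable at baseline level for at least 14 days, "the dose can be re-escalated to the next dose level at the discretion of the investigator".
- **The DLT result is at risk.** See the verdict.

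**Conclusion.** The concern holds in a limited form. Section 7.1.2 and Table 19 are inconsistent for two Grade 4 event types (posterior uveitis and AST/ALT) and unclear for three (rash, nausea/vomiting, all other related events). Diarrhea is unaffected.

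The consequence is for participant safety and consistent conduct, not for the statistics. Under the definition in Protocol Sections 4.1.1 and 9.4.2, DLT status follows from the event and its attribution, not from a later decision to restart. DLT status and the primary endpoint are therefore unaffected. The documents give no expected frequency of Grade 4 events, so none is claimed, and the study plans at most six evaluable participants. This is a minor correction.

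The conclusion assumes that the absence of [e] from the two rows is meaningful. If it is a slip, the wording still needs correcting, in Table 19 as well.

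**What to change.** Reword the bullet in Section 7.1.2 to: *Grade 4 or life-threatening adverse event for which Table 19 requires permanent discontinuation (except with approval from the sponsor's medical monitor where footnote [e] of Table 19 applies, and under its conditions)*. Grade 4 posterior uveitis and Grade 4 AST/ALT then have no restart, and the other three event types follow [e].

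Attaching [e] to the Grade 4 AST/ALT row alone would not work. Those values also meet the row for above 8 × ULN (bilirubin at or below 2 × ULN) or the row for above 5 × ULN (bilirubin above 2 × ULN), both permanent stops without [e]. The conflict would only move inside Table 19.

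The cost is one bullet of protocol wording. The downside is that the medical monitor loses unconditioned discretion over individual cases.
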